ATTACHMENT 1: EXAMPLE OF INFORMED CONSENT FORM

ATTACHMENT 2: CORMATRIX ECM FOR CAROTID REPAIR IFU

ATTACHMENT 3: DRAFT CASE REPORT FORMS

EXECUTIVE SUMMARY

TITLE OF REGISTRY:	CorMatrix® ECM® for Carotid Repair Following Endarterectomy Registry
PROTOCOL NUMBER:	11-PR-1021
OBJECTIVES:	To capture and assess device performance data from subjects undergoing patch angioplasty of the carotid artery following carotid endarterectomy using the CorMatrix ECM for Carotid Repair per its FDA cleared Indications for Use. To provide an ongoing post-market surveillance mechanism to document clinical outcomes on the use of the CorMatrix ECM for Carotid Repair.
REGISTRY DESIGN:	A multi-center, prospective, single-arm, post-market, observational registry of subjects receiving the CorMatrix ECM for Repair for patch angioplasty following carotid endarterectomy (CEA) procedures.
ENROLLMENT:	Up to 230 subjects may be enrolled from up to ten U.S. clinical sites.
INCLUSION CRITERIA:	Subjects must be undergoing carotid endarterectomy with patch angioplasty closure. Subject's operative surgeon intends to use CorMatrix ECM as the patch material for closure of the carotid artery per its FDA cleared Indications for Use. The subject must possess the ability to provide written Informed Consent. The subject must express an understanding and willingness to fulfill all of the expected requirements of this clinical protocol.
EXCLUSION CRITERIA:	Subjects with a known sensitivity to porcine material.
REGISTRY PROCEDURES:	Baseline clinical evaluation and standard follow-up evaluations, including carotid duplex imaging, at 1 to 3-months, 6-months, 12-months, and 24-months postprocedure. Follow-up data will be collected and entered by site personnel in SUGAR COMMUNITY EDITION, electronic data capture system.
OUTCOME MEASURES:	Carotid procedure and device related adverse events to determine device performance data will be collected.
STATISTICAL ANALYSIS:	Descriptive analyses will include overall subject characteristics and outcomes.

REGISTRY CONTACTS	
SPONSOR	CorMatrix Cardiovascular, Inc. [name] [name] [name] [contact] Email: [contact] [contact] [contact]

REVISION HISTORY	
REVISION	DESCRIPTION OF CHANGE
REVISION A JANUARY 24, 2012	INITIAL RELEASE
REVISION B FEBRUARY 7, 2018	PROVIDED INFORMATION ON ELECTRONIC DATA CAPTURE

1.0 INTRODUCTION

1.1 BACKGROUND

Ischemic stroke caused by carotid artery atherosclerosis constitutes major morbidity, mortality, and health care expenditure. Carotid endarterectomy (CEA) is performed to remove atherosclerotic plaque and reduce stroke risk. CEA has been studied extensively within the context of the patient's symptomatic status and degree of carotid stenosis, or narrowing. It has been shown to reduce longer-term risks of stroke in patients without neurologic symptoms and those with prior transient ischemic attacks (TIA) and non-disabling stroke (ACAS/ECST/NASCET/ACST) who have hemodynamically significant carotid stenosis. As such a studied procedure, technical aspects of its performance have been scrutinized. After the endarterectomy portion of the procedure is performed, the arteriotomy must be closed. This can be done by primary closure using suture to reapproximate the longitudinal artery opening, or with a patch. This is known as "patch angioplasty." Patch angioplasty has evolved over time, and it is now widely accepted that use of a patch for closure significantly reduces the risks of carotid restenosis, stroke, and death.¹ There are several materials, which have been utilized for patch closure after CEA. These include autogenous saphenous vein, cervical veins, glutaraldehyde-treated bovine pericardium, and synthetic materials (i.e., ePTFE, Dacron, etc.). However, currently available synthetic or chemically treated patch materials may induce scar tissue formation leading to restenosis and can lead to a higher risk of infection.² The CorMatrix ECM for Carotid Repair is an attractive vascular patch material due to its ability to be remodeled into healthy native tissue.

1.2 DEVICE DESCRIPTION

The CorMatrix ECM for Carotid Repair is an acellular, natural collagen construct, derived from the porcine small intestine submucosa that has demonstrated the ability to provide a scaffold for cells for remodeling various tissues following implantation into subjects.

The CorMatrix ECM for Carotid Repair is supplied in a six-ply sheet, which can be cut to size as the physician deems necessary for the specific procedure to be performed. The CorMatrix ECM for Carotid Repair is provided in a lyophilized, sterile state and is for single use only.

1.3 REGULATORY STATUS

CorMatrix Cardiovascular, Inc. received U.S. FDA 510(k) premarket

¹ Awad IA and Little JR. Patch angioplasty in carotid endarterectomy. Advantages, concerns, and controversies. *Stroke* 1989;20:417-22.

² Bond R et al. Systematic review of randomized controlled trials of patch angioplasty versus primary closure and different types of patch materials during carotid endarterectomy. *J Vasc Surg* 2004;40:1126-35.

clearance (K111187) for the CorMatrix ECM for Carotid Repair on July 26, 2011.

1.4 INDICATIONS FOR USE

The CorMatrix ECM for Carotid Repair is intended for use as a patch material for vascular reconstruction and repair of the carotid artery, including patch closure following carotid endarterectomy and suture line buttressing.

2.0 REGISTRY OBJECTIVES

The objective of this registry is to capture and assess device performance data from subjects undergoing patch angioplasty of the carotid artery following carotid endarterectomy using the CorMatrix ECM for Carotid Repair per its FDA cleared Indications for Use. This registry provides an ongoing post-market surveillance mechanism to document clinical outcomes on the use of the CorMatrix ECM for Carotid Repair.

3.0 REGISTRY DESIGN

This is a multi-center, prospective, single-arm, post-market, observational registry of subjects receiving the CorMatrix ECM for Carotid Repair for patch angioplasty following carotid endarterectomy procedures.

This post-market registry may involve up to ten U.S. clinical sites and up to 230 subjects. Data will be collected through the 24-month follow-up. The data may also be used for publications.

3.1 OUTCOME MEASURES

3.1.1 Performance: Observe the performance and clinical outcome of the CorMatrix ECM for Carotid Repair for patch angioplasty following carotid endarterectomy. Collected data will include both carotid procedure and device related adverse events to determine device performance data.

3.2 SAMPLE SIZE

Up to 230 subjects may be enrolled in this registry.

3.3 REGISTRY DURATION/FOLLOW-UP

All subjects enrolled in this registry will be evaluated preoperatively and followed from their treatment date through 24-months postprocedure. Subjects will have a baseline standard clinical evaluation and standard follow-up evaluations, including carotid duplex imaging, at 1 to 3-months, 6-months, 12-months, and 24-months postprocedure. If intraoperative completion duplex or other imaging (i.e., CTA, MRA, arteriography) is performed, data should be collected, but this is not mandatory.

3.4 REGISTRY POPULATION AND ELIGIBILITY CRITERIA

Subjects must meet the following requirements in order to be eligible for enrollment in the registry:

3.4.1 Inclusion Criteria

All subjects are required to meet the following inclusion criteria in order to be considered eligible for participation in this registry:

- Subjects must be undergoing carotid endarterectomy with patch angioplasty closure.
- Subject's operative surgeon intends to use CorMatrix ECM as the patch material for closure of the carotid artery per its FDA cleared Indications for Use.
- The subject must possess the ability to provide written Informed Consent.
- The subject must express an understanding and willingness to fulfill all of the expected requirements of this clinical protocol.

3.4.2 Exclusion Criteria

Subjects will be excluded from participating in this registry if the following exclusion criterion is met:

- Known sensitivities to porcine material

3.5 PROCEDURAL OVERVIEW

After a subject has undergone the preoperative evaluation, has been determined to be eligible for the registry and signed an Informed Consent Form, he or she will be considered enrolled in the registry. After enrollment, the subject will undergo a standard carotid interventional procedure including carotid endarterectomy. The subject's carotid arteriotomy site will be closed using the CorMatrix ECM for Carotid Repair. The surgeon will implant the CorMatrix ECM for Carotid Repair according to the FDA cleared Instructions for Use.

3.6 REGISTRY SITES

Up to ten U.S. clinical sites may participate. Sites will be selected due to ability to provide expertise in carotid endarterectomy and carotid duplex imaging.

3.7 INSTITUTIONAL REVIEW BOARD APPROVALS

Before any subject can be enrolled in this registry, the Institutional Review Board (IRB) for the specific institution must approve the protocol and the Informed Consent Form to be used at that site. A subject cannot be asked

to sign the Informed Consent Form until the registry has been fully approved by the institution's IRB. The Sponsor will require a copy of any IRB correspondence, as well as the final approval letter and the final approved Informed Consent Form, from each IRB.

3.8 REGISTRY CONDUCT

This registry will be performed in accordance with Title 21 Code of Federal Regulations Parts 50 and 56 and other relevant FDA regulations and the relevant sections of the ICH Guidelines for Good Clinical Practices.

The principles of the Declaration of Helsinki have been addressed in the design of the registry, consideration of the risk and benefits to the subjects, selection of the site and Investigators to conduct the registry, measures taken to protect the health and rights of the human subjects, and registration of the registry in a publicly accessible database.

4.0 SUBJECT ENROLLMENT INFORMATION

4.1 INFORMED CONSENT

Subjects cannot be asked to sign the Informed Consent Form until the registry has been fully approved by the respective institution's IRB and the Sponsor has received and reviewed the specific IRB approved Informed Consent Form. When the Investigator has determined the eligibility of a specific subject to enter the registry, the Informed Consent Form must be completed. The Informed Consent Form must be read by the subject, the subject's questions answered and the form signed and dated by the subject, before the surgical procedure can be performed. All subjects are to receive copies of their Informed Consent Form.

4.2 SURGEON TRAINING

Surgeons will be trained prior to subject enrollment by CorMatrix personnel according to the FDA cleared CorMatrix ECM for Carotid Repair Instructions for Use.

4.3 COVERAGE OF EXPENSES

Subjects will not be reimbursed or compensated for participating in the registry; the procedure will be billed to medical insurance as per standard procedure.

4.4 CONFIDENTIALITY

Confidentiality of subjects will be maintained throughout the registry. A unique identification code will be assigned to each subject participating in this registry. Any data that may be published in abstracts, scientific journals, or presented at medical meetings will reference a unique subject code and will not reveal the subject's identity. The Sponsor will make

every reasonable effort to protect the confidentiality of the subjects participating in the registry.

5.0 DATA COLLECTION PROCEDURES

5.1 PREOPERATIVE EVALUATION

The following information will be collected for each subject: demographics, risk factors, preoperative medications (anti-platelets, anti-coagulants, anti-arrhythmics, anti-hypertensives, betablockers, and statins) taken within approximately 3 months prior to the procedure and verification that the subject meets inclusion/exclusion criteria specified in the protocol. A carotid duplex imaging or approved testing is required preoperatively (within 60 days of the procedure) to measure the percentage of carotid artery stenosis.

5.2 OPERATIVE EVALUATION

The carotid endarterectomy should be performed per the surgeon and institution's standard CEA procedures. Specific data on the CEA procedure as well as the CorMatrix ECM will be collected. Also, carotid procedure and/or device related adverse events will be documented on appropriate CRFs in SUGAR COMMUNITY EDITION, electronic data capture system.

5.3 POSTOPERATIVE EVALUATION

Postoperative data from the end of the CEA procedure until the subject is discharged from the hospital will be collected. Medications (anti-platelets, anti-coagulants, anti-arrhythmics, anti-hypertensives, betablockers, and statins) and carotid procedure and/or device related adverse events will be documented on appropriate CRFs in SUGAR COMMUNITY EDITION, electronic data capture system.

5.4 1 TO 3-MONTH FOLLOW-UP EVALUATION

Subjects will have a follow-up evaluation at 1 to 3 months after the carotid procedure. Information will be collected regarding the subject's health status, medications (anti-platelets, anti-coagulants, anti-arrhythmics, anti-hypertensives, betablockers, and statins) and the occurrence of any carotid and/or device related adverse events. A carotid duplex imaging or approved testing is required and the data will be collected on appropriate CRFs in SUGAR COMMUNITY EDITION, electronic data capture system. Results of any additional anatomic imaging performed should be recorded.

5.5 6-MONTH FOLLOW-UP EVALUATION (\pm 1 MONTH)

Subjects will have a follow-up evaluation 6 months (\pm 1 month) after the carotid procedure. Information will be collected regarding the subject's health status, medications (anti-platelets, anti-coagulants, anti-arrhythmics, anti-hypertensives, betablockers, and statins) and the occurrence of any carotid and/or device related adverse events. A carotid duplex imaging or approved testing is required and the data will be collected on appropriate CRFs in SUGAR COMMUNITY EDITION, electronic data capture system. Results of any additional anatomic imaging performed should be recorded.

5.6 12-MONTH FOLLOW-UP EVALUATION (\pm 1 MONTH)

Subjects will have a follow-up evaluation 12 months (\pm 1 month) after the carotid procedure. Information will be collected regarding the subject's health status, medications (anti-platelets, anti-coagulants, anti-arrhythmics, anti-hypertensives, betablockers, and statins) and the occurrence of any carotid and/or device related adverse events. A carotid duplex imaging or approved testing is required and the data will be collected on appropriate CRFs in SUGAR COMMUNITY EDITION, electronic data capture system. Results of any additional anatomic imaging performed should be recorded.

5.7 24-MONTH FOLLOW-UP EVALUATION (\pm 1 MONTH)

Subjects will have a follow-up evaluation 24 months (\pm 1 month) after the carotid procedure. Information will be collected regarding the subject's health status, medications (anti-platelets, anti-coagulants, anti-arrhythmics, anti-hypertensives, betablockers, and statins) and the occurrence of any carotid and/or device related adverse events. A carotid duplex imaging or approved testing is required and the data will be collected on appropriate CRFs in SUGAR COMMUNITY EDITION, electronic data capture system. Results of any additional anatomic imaging performed should be recorded.

5.8 REGISTRY EXIT

Subjects will be exited from the registry following their scheduled 24-month follow-up evaluation, or earlier if the subject withdraws from the registry, or his/her participation is discontinued by the Investigator, or death. The date each subject completed the registry per this protocol, or if not, then the date the subject exited from the registry and the primary reason should be recorded. Any subject who experiences a serious carotid and/or device related adverse event that is ongoing at the time of exit will be followed by the physician until the adverse event is resolved or the subject is medically stable in the opinion of the Investigator.

5.9 DISCONTINUED SUBJECTS

Subjects are considered enrolled once they have signed the informed consent form. There are three categories of discontinued subjects: those who withdraw from the registry prior to any activities related to the treatment procedure; those in whom implantation of the CorMatrix ECM for Carotid Repair does not occur due to clinical concerns at the time of operation; and those who elect to withdraw from the registry after implantation of the CorMatrix ECM device. Discontinued subjects will be followed by the physician until they are considered to be medically stable.

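### An abandoned patch attempt without a serious adverse event is recorded but enters no planned device-performance rate (5.9 read with 11.2)

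*Combined protocol and SAP*

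**What the plan says.** Enrolment precedes the operation. Section 5.9 states: "Subjects are considered enrolled once they have signed the informed consent form". Section 3.5 agrees: after evaluation, eligibility and consent, "he or she will be considered enrolled in the registry". Eligibility in 3.4.1 rests on intent, in that the "operative surgeon intends to use CorMatrix ECM as the patch material for closure of the carotid artery". An enrolled subject who does not receive the patch is therefore a foreseeable case.

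Section 5.9 provides for it with one of three discontinuation categories: "those in whom implantation of the CorMatrix ECM for Carotid Repair does not occur due to clinical concerns at the time of operation". Clinical concerns are not defined, and nothing distinguishes a patch that was opened, cut or sutured and then given up from one that never left its package. On what happens next, 5.9 says: "Discontinued subjects will be followed by the physician until they are considered to be medically stable".

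The cohort is described in two ways. Section 3.0 speaks of a "registry of subjects receiving the CorMatrix ECM for Carotid Repair for patch angioplasty following carotid endarterectomy procedures", while 3.3 says: "All subjects enrolled in this registry will be evaluated preoperatively and followed from their treatment date through 24-months postprocedure".

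Section 11.2 takes registry completers as the denominator for categorical variables, with an exact 95% confidence interval. It lists related serious adverse events and leaves Kaplan-Meier analysis to be done if judged necessary, naming no event or population. Section 3.1.1 describes performance through procedure- and device-related adverse events. No implant-success measure and no analysis set (enrolled, attempted, implanted) is defined.

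**The concern.** The registry exists to assess how the device performs. A patch that tears or handles badly in theatre and is replaced by another material is a performance result. Under 5.9 that subject is discontinued, so he or she cannot be a completer and leaves every percentage built on the 11.2 denominator. If the event is not serious, the 11.2 listing does not pick it up either.

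Among completers, implant success is then close to 100% by construction, however many attempts were abandoned. The omission runs in one direction, in the device's favour. It arises on the operating table, but it reaches the results only because 5.9 and 11.2 act together.

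**Working it through.** The plan has no figure to reproduce: 230 is an enrolment ceiling without a derivation, and no non-implantation rate is given. The check is therefore a trace through the sections, followed by an illustration.

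**Trace of one subject: patch opened, abandoned, no serious adverse event**

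| Step | Section | Result |
|---|---|---|
| Consent signed | 3.5, 5.9 | Enrolled |
| Operative and device data, related adverse events | 5.2, 6.2 | Recorded |
| Device failure, malfunction or technical observation, if it meets a definition | 6.1, 10.4 | Failure and malfunction reports kept by the sponsor |
| Discontinued for clinical concerns | 5.9 | Same category as a patch never opened |
| Exit date and primary reason | 5.8 | Recorded |
| Categorical percentages | 11.2 | Not a completer, so not in the denominator |
| Adverse event listing | 11.2 | Serious events only, so not listed |
| Final report | 11.3 | Covered by a general summary of the data, with no count, denominator or reason specified |

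The subject is recorded at each collection step and counted in no planned rate.

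**Illustration**

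Inputs: N = 230 (3.2) and the exact interval (11.2, taken as Clopper-Pearson). Assumed, not in the documents: a abandoned attempts, from 3 to 23 (3/230 = 1.3% to 23/230 = 10%); 10 events among the other subjects; every other subject implanted and completing.

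- Left out: 10/(230 − a)
- Counted as device-use failures: (10 + a)/230
- Implant success over attempted: (230 − a)/230

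| a | Left out (95% CI) | Counted (95% CI) | Implant success (95% CI) |
|---|---|---|---|
| 3 | 10/227 = 4.4% (2.1 to 8.0) | 13/230 = 5.7% (3.0 to 9.5) | 227/230 = 98.7% (96.2 to 99.7) |
| 12 | 10/218 = 4.6% (2.2 to 8.3) | 22/230 = 9.6% (6.1 to 14.1) | 218/230 = 94.8% (91.1 to 97.3) |
| 23 | 10/207 = 4.8% (2.3 to 8.7) | 33/230 = 14.3% (10.1 to 19.6) | 207/230 = 90.0% (85.4 to 93.6) |

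The left-out rate hardly moves as abandoned attempts rise from 3 to 23, so the planned percentages could not reveal the difference. The combined rate in the third column only shows scale; it is not proposed as an endpoint.

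**Arteries closed with another material for a non-clinical reason**

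If 12 such subjects stayed in the denominator with no events, the rate would be 10/230 = 4.35% against 10/218 = 4.59% among implanted subjects. With 23, it would be 4.35% against 10/207 = 4.83%. This effect is small beside the first.

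**The case against.** The strongest reply is that nothing is lost. Operative and device data are collected (5.2), related events run from enrolment to exit (6.2), the exit reason is recorded (5.8), and device failure, malfunction and technical observation are defined (6.1). The sponsor keeps failure and malfunction reports (10.4), the serious-event listing is not limited to completers (11.2), and the final report summarises all data (11.3). This is also a descriptive registry with no hypothesis or performance goal, and the draft case report forms are not shown, so the operative form may already carry the needed field.

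Most of that stands. A reader might infer that abandoned attempts vanish from the registry, or that 5.9 alone removes them. The documents support neither: the data exist, and the loss from the rates needs the 11.2 denominator. What remains is that recording an event does not commit anyone to reporting it. No section promises a count of abandoned attempts, a denominator for them, or a tabulation of non-serious device failures.

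A reader might also infer that subjects closed another way for supply, size or preference must stay for 24 months, because they fit none of the 5.9 categories and 3.3 covers everyone enrolled. That is an inference from silence. Section 5.8 allows exit when "his/her participation is discontinued by the Investigator, or death" applies, without limiting the investigator's reason, and 3.0 describes subjects who receive the device. The sections leave these subjects without a stated rule, so up to ten sites may handle them differently. They do not prescribe retention.

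**Conclusion.** The point holds as a reporting gap. An attempted and abandoned patch without a serious adverse event is recorded but enters no planned device-performance rate, and 5.9 does not separate it from a patch never tried. The direction favours the device.

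The size cannot be stated from the documents. Under the assumed counts, the gap between leaving the attempts out and counting them runs from 5.7 − 4.4 = 1.3 percentage points (3 attempts) to 14.3 − 4.8 = 9.5 points (23 attempts). If abandoned attempts are rare, the effect is negligible, but the planned percentages would not show that either. Retention of arteries closed another way is secondary: it is not prescribed, and its illustrated effect is at most 4.83 − 4.35 = 0.48 points.

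This does not undermine the registry. It is an inexpensive change that decides whether intraoperative device failure is visible in the results.

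**What to change.** **Section 5.9.** Classify non-implanted subjects as:
- (i) ECM not attempted: package not opened for that subject, for any reason;
- (ii) ECM attempted: package opened or prepared, but the ECM not left in place, with the reason recorded.

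Contact with the artery should not be the test. A sheet that tears while being trimmed would then count as not attempted and leave the denominator.

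**Section 11.2.**
- Report implant success as the number left in place over all attempted, with the exact 95% confidence interval, regardless of registry completion.
- List each category (ii) subject with the reason and any device failure or malfunction.
- Report post-implant device outcomes among implanted subjects, so that arteries closed with another material are not counted as CorMatrix outcomes. Because implant success is reported beside them over all attempted, abandoned attempts stay visible.

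**Sections 3.0, 3.3 and 5.9.** Reconcile the wording on subjects closed another way for a non-clinical reason, who can already exit under 5.8. Leave the care and follow-up of all non-implanted subjects as they stand.

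**Cost.** Short edits to these sections and one operative case report form field, if it is not already present. The report will also show an implant-failure figure that the present plan does not require.
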